Pre-operative condition and patients outcomes will be assessed using standardized and validated measures. The primary endpoint of a mRS score will be obtained at least 90 days following treatment and again at 1 year following treatment. NIHSS score will be obtained in the emergency room before the treatment, within 24 h of treatment, and before discharge. The person who will obtain the NIHSS will be certified to obtain it. Adequacy of revascularization will be assessed at the end of treatment by the treating physician according the modified thrombolysis in cerebral infarction (mTICI) scale (see Appendix). All of these measures are standards for care and trials of acute ischemic stroke. [8-10] All case report forms will be maintained by the primary investigator at the local site, and stored within locked cabinets. The personal identifying information on the case report forms will be deidentified and assigned a code before being transferred to Akron General Medical Center for transfer of the data to a de-identified database which will be used for analysis.

IV. DATA COLLECTION

Version: 6.0

A. How and what data will be collected

Data related to patient demographics, stroke risk factors, condition prior to treatment, time of treatment, and outcomes will be collected for each patient. Data on demographics will include sex, age, and race. Data on stroke risk factors will include history of hypertension, blood pressure, prior heart attack, arrhythmias, diabetes, glucose (sugar) level at admission, and obesity. Data on condition prior to treatment will include NIHSS score determined in the emergency room. Data on time of treatment will include time from symptoms to arrival at emergency room, time to start of DCA, and time to end of the procedure. Data on outcomes will include mRS at 3 months, mRS at 1 year, NIHSS score within 24 hours and at discharge, and complications brain edema and intra-cranial hemorrhage. Other parameters within these categories could be acquired as deemed necessary for analysis of the data.

V. DATA ANALYSIS

A. Sample Size Considerations

Phase I

A power analysis has been performed based on the previous retrospective analyses of the relationship between outcomes and the CIS for phase I. The sample size was calculated for the influence of the combination of CIS and revascularization on good outcomes (mRS \leq 2) based on the following assumptions.

- The percentage of patients with fCIS will be 60%

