- The percentage of patients with good revascularization will be 50%
- The rate of good outcomes for the combination of fCIS and good revascularization is assumed to be 70%
- The rate of good outcomes for the combination of fCIS and poor revascularization is assumed to be 20%
- The rate of good outcomes for the combination of pCIS and good revascularization is assumed to be 20%
- The rate of good outcomes for the combination of pCIS and poor revascularization is assumed to be 10%

The assumptions provide the following power analysis:

- $\alpha = 0.05$ for overall analysis and set to 0.025 for subgroup analysis comparing fCIS and good revascularization to all other groups due to multiple comparisons
- power = 0.90
- Needed Sample size = 54 patients
- An additional 6 patients completing the trial are budgeted due to risk of errors in estimated outcomes. An additional 15-20 patients are expected to be enrolled due to patients lost to the 90 day follow up and/or deviations from the protocol.

Phase II

Phase II will be an exploratory study evaluating the rates for good outcomes for patients with pCIS treated with IVT plus IAT vs. IVT (or other standard of care) only. The rate of good outcomes is expected to be approximately 13% for the IAT group with revascularization. The investigators have no prior data on expected rates of good outcomes for patients with pCIS treated with IVT only. The best possible outcome rate would be on

Version: 6.0

the order of 25% noted previously for untreated acute ischemic stroke. Due to the low levels of good outcomes, the investigators acknowledge the study will be underpowered to detect a difference between the two treatment groups for a total sample size of 30. Phase II will serve as a pilot study to initially establish estimates of rates of good outcomes for pCIS patients treated with IVT only for design of a larger prospective study.

Genetic Analysis

Genetic analysis will be performed based on the following:

- Genetic and expression analysis for the two groups based on their collateral score
- Adjust groups for cardiovascular/stroke risk factor presence and other known confounding conditions
- High density SNP array analysis will be performed for common and rare alleles
 against known collateral-related genes that have been identified in mice. These
 include human RABEP2 and its isoform RABEP1 and related gene pathways;
 VEGFA, FLK1 and their related gene pathways; NOTCH, DLL4, ADAM10,

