 ADAM17, CNX37 and their related gene pathways.
- Subgroup analysis will be performed for ethnicities.
- Taqman assays and/or exome sequencing of significantly associated SNPs and/or genes.
- Pending results, a future validation study will follow this discovery study by increasing the sample size.

B. Statistical Methodology

Data for the proposed study will be analyzed using comparison of proportions and multivariable logistic regression. Analysis of proportions based on Fisher exact tests will be used to compare rates of good outcomes between the fCIS and pCIS groups as the primary end point for phase I. The influence of successful revascularization on outcomes for patients with fCIS or pCIS will also be analyzed using Fisher exact tests as the secondary end point.

Binary and/or ordinal multiple logistic regression analyses will be used to evaluate the influence of multiple parameters on the likelihood of a good outcome. These parameters will include CIS, mTICI score, NIHSS score, time to revascularization, age, sex, history of diabetes mellitus, history of high blood pressure, history of coronary artery disease. The same analyses will be performed for phase II, instead focusing on the treatment groups rather than the CIS classification.

VI. DATA AND SAFETY MONITORING PLAN

A. Describe any provisions for monitoring the data for safety

A safety committee will monitor the data. The safety committee will be composed of at least 3 voting members. At least two members will be neurologists, neuroradiologists or neurointerventionalists with experience treating acute ischemic stroke who are not investigators at any of the sites. These members will not be affiliated with the institution of the principal investigator, any sub- investigator, or Akron General Medical Center. At least one member with a background in biostatistics who is not an investigator or affiliated with Akron General Medical Center will also be on the committee.

For phase I, the only deviations in normal standards of care are:

Version: 6.0

- 1- the extra few minutes for full DCA for some centers as opposed to injecting only the occluded vessel
- 2- Adding IAT to treatment of patients seen between 6 and 24 hours of onset of symptoms.

The safety committee will be looking at known potential complications for IAT in both fCIS and pCIS groups. These include:

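### The 90% power at 54 patients comes from a CIS-by-revascularization calculation; the declared primary test (Fisher, fCIS vs pCIS) has about 61% power at 54 and 65% at 60

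*Combined protocol and SAP*

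**What the plan says.** Section V.A (Sample Size Considerations, Phase I) gives the basis of the calculation: "The sample size was calculated for the influence of the combination of CIS and revascularization on good outcomes". It assumes 60% of patients with fCIS and 50% with good revascularization. The assumed good-outcome rates are:

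- 70% for fCIS with good revascularization
- 20% for fCIS with poor revascularization
- 20% for pCIS with good revascularization
- 10% for pCIS with poor revascularization

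An alpha of 0.05 applies "for overall analysis and set to 0.025 for subgroup analysis comparing fCIS and good revascularization to all other groups due to multiple comparisons". The stated power is 0.90, and the result is "Needed Sample size = 54 patients". Six more completers are added, making 60, which agrees with section III.A.

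Section V.B (Statistical Methodology) then says of Phase I that "Fisher exact tests will be used to compare rates of good outcomes between the fCIS and pCIS groups as the primary end point". The effect of revascularization within the CIS groups is the secondary end point. Neither a four-group test nor the contrast of fCIS with good revascularization against everyone else appears among the V.B end-point tests.

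**The concern.** The sample size was set for one question and the primary end point asks another. The four-group calculation draws most of its strength from a single group, fCIS with good revascularization, at 70%. The primary test pools that group with the fCIS patients who were poorly revascularized (20%), which dilutes the difference. The stated power of 0.90 therefore need not carry over to the primary test, yet it is the only Phase I power figure given, and a reader will take it to describe the primary end point.

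The plan's admissions of low power (sections III.A, V.A and VII) concern Phase II only. If the primary test is materially weaker than 90%, a non-significant Phase I result would be given more weight as evidence against CIS than it deserves.

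**Working it through.** **Inputs**, all from V.A: fCIS share 0.60; good revascularization 0.50, taken as equal in both CIS groups; rates 0.70, 0.20, 0.20 and 0.10. The four groups then have weights 0.30, 0.30, 0.20 and 0.20. Sidedness is not stated, so two-sided is assumed and one-sided is shown as a check.

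**1. Reproducing 54.** The plan does not name the test behind this figure. Two candidates reach it or come close.

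*Four-group chi-square, 3 df, alpha 0.05.*
- Overall rate: 0.30×0.70 + 0.30×0.20 + 0.20×0.20 + 0.20×0.10 = 0.33.
- Effect size: w² = Σ weight×(rate − 0.33)² / (0.33×0.67) = (0.04107 + 0.00507 + 0.00338 + 0.01058)/0.2211 = 0.0601/0.2211 = 0.272, so w = 0.521.
- Noncentral chi-square power with noncentrality N×w²: 0.899 at N = 52, 0.905 at 53, 0.911 at 54.

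*fCIS with good revascularization against all others, two-sided 0.025.*
- Rate in all others: (0.30×0.20 + 0.20×0.20 + 0.20×0.10)/0.70 = 0.12/0.70 = 17.1%.
- The pooled formula for 70% vs 17.1% with continuity correction needs 16 in the smaller group; 16/0.30 = 53.3, rounded up to 54.
- Exact Fisher power at 16 vs 38 is 0.925.

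Both candidates use the CIS-by-revascularization groups, so the stated figure is sound for that purpose.

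**2. Rates for the primary comparison.**
- fCIS: 0.5×0.70 + 0.5×0.20 = 0.45
- pCIS: 0.5×0.20 + 0.5×0.10 = 0.15

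**3. Power of the primary test.** Enumerate all 2×2 tables and sum Bin(x; n₁, 0.45)×Bin(y; n₂, 0.15) over those with Fisher p ≤ 0.05.

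| Completers (fCIS/pCIS) | Fisher, two-sided 0.05 | Fisher, one-sided 0.05 |
|---|---|---|
| 54 (32/22) | 0.613 | 0.677 |
| 54 (33/21) | 0.588 | 0.690 |
| 60 (36/24) | 0.646 | 0.725 |
| 60 (30/30) | 0.645 | 0.757 |
| 60 (42/18) | 0.586 | 0.677 |
| 105 (63/42) | 0.905 | not computed |

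- Letting the 60/40 split vary at random gives about 0.59 at 54 and 0.64 at 60 (two-sided).
- The pooled normal approximation, two-sided 0.05, gives 0.647 at 54 and 0.698 at 60. It needs 100 patients for 90%, or about 114 with continuity correction.
- The chance of missing the assumed effect is 1 − 0.646 = 35% at 60 and 1 − 0.613 = 39% at 54.

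**4. Sensitivity to the share with good revascularization**, same four rates, two-sided Fisher:

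| Good revascularization | fCIS vs pCIS | N = 54 | N = 60 |
|---|---|---|---|
| 50% (plan) | 45% vs 15% | 0.613 | 0.646 |
| 60% | 50% vs 16% | 0.711 | 0.750 |
| 70% | 55% vs 17% | 0.791 | 0.835 |
| 80% | 60% vs 18% | 0.855 | 0.900 |
| 90% | 65% vs 19% | 0.906 | 0.943 |

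**The case against.** The strongest reply is that nothing is miscalculated or hidden. V.A says openly that the calculation concerns the combination of CIS and revascularization, 54 reproduces for that purpose, and the plan never claims 90% for fCIS against pCIS. That is fair: the sum is right, and the fault is that it does not belong to the declared primary test. Because the test behind 54 is not named, attributing it to either candidate is an inference. Both rest on the same four groups, so the conclusion does not turn on it.

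A second reply is that 50% good revascularization is pessimistic, since section I.C cites recanalization rates up to 80–90%. At 80% the primary test would have about 0.90 at 60 completers. This is a real dependence, but 50% is the plan's own assumption and the one that yields 54.

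Third, 61% applies only if the six-patient buffer is lost, so 65% is the operative figure. This is correct. The further 15–20 enrolments replace losses and deviations and do not add completers.

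Fourth, launching Phase II depends on pCIS outcomes and safety committee review (sections VI and VIII.B), not on this p-value, and V.B also plans a regression containing both CIS and mTICI. These points limit the consequences. They do not supply the primary test with the stated power.

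**Conclusion.** The concern holds. Under the plan's own assumptions, the Phase I primary test has about 65% power at the 60 planned completers and 61% at 54. The stated 0.90 describes the CIS-by-revascularization analyses. About 105 completers would be needed for 90% with Fisher's test.

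These figures assume a two-sided 0.05 level, a 60/40 CIS split and 50% good revascularization in each CIS group. The plan gives only an overall 50%; equal shares are also what the reproduction of 54 uses. If good revascularization were more common among fCIS patients, the pooled difference would be wider and power higher. One-sided testing (0.725 at 60) and balancing the groups (0.645 at 30/30, two-sided) do not restore 90%.

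**What to change.** In V.A, state the power of the declared primary test: about 65% at 60 completers and 61% at 54, for 45% vs 15%, two-sided Fisher at 0.05. Name the test that produced 54, and say that the 0.90 applies only to the four-group analysis and to the contrast of fCIS with good revascularization against all others. Show how primary-test power varies with the revascularization rate. The cost is protocol wording and a less favourable stated power, with no extra patients.

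Optionally, replace Fisher's test with Boschloo's unconditional exact test for the primary comparison. At 36/24 its power is 0.699 with true size 0.049, against 0.646 and about 0.035 for Fisher. This is one line of analysis code; it narrows the gap but does not close it.

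The alternative is to make the contrast that was powered the primary one (Fisher power about 0.95 at 60, two-sided 0.025). That changes the question, because revascularization is graded only at the end of treatment whereas CIS is meant for selection beforehand. Keeping the pooled comparison at 90% power would instead need about 45 more completers (105 − 60).

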- a. Lengthen the time window of treatment for patients with fCIS from 6 hours to 24 hours. In doing so, we will offer useful treatment to patients who would otherwise be denied treatment under current standards.
- b. Encourage focusing on achieving good revascularization rather than limiting time during IAT for patients with fCIS.
- c. Improve the percentage of good outcomes in the treated population
- d. Save patients with pCIS from complications due to brain edema and intra-cranial hemorrhage that could potentially result from IAT
- e. Save the health care system the costs of futile treatment of patients with pCIS.

III. METHODS

A. Study Design:

Version: 6.0

The current study focuses on patients with acute ischemic stroke due to a blockage of the intracranial internal carotid artery or middle cerebral artery (M1). The study will be performed prospectively in up to 6 stroke centers. Akron General Medical Center is the primary institution for development of the study and data analysis for this multicenter trial. To participate in the study, all centers need to meet certain qualified requirements which include:

- One neurointerventionalist with 6 years' experience in performing IAT with multiple devices.
- Demonstrate coverage of the comprehensive stroke center 24 hours a day. The proposed study will be carried out over a period of 4 years from the initial approval date. Informed consent will be obtained for each patient, as described in section VIII. The study will be carried out in 2 phases (Figure 1).

Phase I will compare outcomes between treated patients with fCIS and pCIS. All eligible patients will be assessed by a full diagnostic cerebral angiogram with dye injection of all potential collaterals. DCA will be used to characterize the CIS. Treatment will be identical for both groups. All patients will be treated with the combination of IAT and the normal standard of care for a patient not receiving IAT (which may include IVT, but not always). The sample size will be set to have 60 patients complete the trial. Distribution of fCIS and pCIS patients will not be forced, but the option to balance groups may be employed if the percentage for one group reaches 70%.

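### Fisher's exact test is valid but conservative at these sample sizes; Boschloo's exact test holds the same 5% limit and adds about 5 points of power to the Phase I primary comparison

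*Combined protocol and SAP*

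**What the plan says.** Section V.B (Statistical Methodology) names one test for every comparison of proportions.

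- Phase I primary: "Analysis of proportions based on Fisher exact tests will be used to compare rates of good outcomes between the fCIS and pCIS groups".
- Phase I secondary: the influence of revascularization within the fCIS and pCIS groups "will also be analyzed using Fisher exact tests as the secondary end point".
- Phase II: "The same analyses will be performed for phase II, instead focusing on the treatment groups rather than the CIS classification".

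Section V.A sets alpha at 0.05 "for overall analysis and set to 0.025 for subgroup analysis comparing fCIS and good revascularization to all other groups". It does not say whether tests are one- or two-sided. It gives "Needed Sample size = 54 patients" at power 0.90, and section III.A states "The sample size will be set to have 60 patients complete the trial". V.A describes Phase II as exploratory and underpowered at 30 patients. The plan does not discuss how conservative Fisher's test is at these sizes, and it names no unconditional alternative.

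**The concern.** Fisher's test conditions on both margins of the 2×2 table. The number of good outcomes is not fixed by design in either phase, and in Phase I the CIS split is not fixed either. In small samples the conditional p-value takes few distinct values, so the true rejection rate under the null falls well below the nominal level.

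Boschloo's test uses the Fisher p-value as its statistic. It raises the rejection threshold as far as possible while the error, maximized over the unknown common rate, stays at or below alpha. Its rejection region contains Fisher's, so at given group sizes its power cannot be lower.

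At stake is power. The trial is small and expects about one eligible patient per center per month at up to six centers (III.C), so power that costs no patients is worth having.

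**Working it through.** **Inputs (V.A, III.A).** "The percentage of patients with fCIS will be 60" per cent and "The percentage of patients with good revascularization will be 50" per cent. Good-outcome rates are 70% (fCIS, good revascularization), 20% (fCIS, poor), 20% (pCIS, good) and 10% (pCIS, poor). Phase II has 30 patients at 1:1, with about 13% expected with IAT and at best about 25% without.

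**Assumptions.** Tests are two-sided. The 50% revascularization share applies in both CIS groups. Phase II splits 15/15. The 0.025 contrast also uses Fisher's test.

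**Derived quantities.**
- fCIS rate: 0.5×70% + 0.5×20% = 45%. pCIS rate: 0.5×20% + 0.5×10% = 15%.
- 60 completers: 36 fCIS and 24 pCIS, splitting by revascularization into 18/18 and 12/12.
- fCIS with good revascularization is 0.6×0.5 = 30% of patients. The remaining 70% have a rate of (0.30×20% + 0.20×20% + 0.20×10%)/0.70 = 17.1%.

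**The plan's 54.** This comes from the 0.025 contrast, not the primary comparison. With p1 = 0.70, p2 = 0.1714, r = 7/3 and pooled rate 0.33:

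n1 = [2.241·√((1+3/7)·0.33·0.67) + 1.282·√(0.21 + 0.142·3/7)]² / 0.5286² = (1.260 + 0.667)²/0.279 ≈ 13.3.

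The continuity correction raises this to 15.9, so 16, and 16/0.30 = 53.3, so 54. A 3-df chi-square over the four cells at 0.05 gives 53, so the source is not certain. The primary contrast (45% vs 15%, 60:40) gives 80 to 132 patients under every variant tried, never 54.

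**Size and power by full enumeration.** For group sizes n1 and n2 and rejection region R:

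Pr(reject | p1, p2) = Σ over (x, y) in R of Bin(x; n1, p1)·Bin(y; n2, p2).

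Maximum size sets p1 = p2 and maximizes over the common rate. Fisher's R is all tables with two-sided p ≤ alpha (probability ordering). Boschloo's R is all tables with Fisher p ≤ c, where c is the largest threshold that keeps maximum size ≤ alpha.

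| Comparison | Groups | Rates | Max size, Fisher | Max size, Boschloo | c | Power, Fisher | Power, Boschloo | Gain (points) |
|---|---|---|---|---|---|---|---|---|
| Phase I primary | 36/24 | 45% vs 15% | 3.5% | 4.9% | 0.064 | 64.6% | 69.9% | 5.2 |
| Secondary, within fCIS | 18/18 | 70% vs 20% | 2.9% | 4.8% | 0.088 | 83.5% | 86.6% | 3.1 |
| Secondary, within pCIS | 12/12 | 20% vs 10% | 2.3% | 4.5% | 0.093 | 2.2% | 6.8% | 4.6 |
| Phase II | 15/15 | 25% vs 13% | 1.8% | 4.3% | 0.100 | 5.7% | 11.6% | 6.0 |
| fCIS with good revascularization vs rest, alpha 0.025 | 18/42 | 70% vs 17.1% | 1.9% | 2.3% | 0.034 | 95.2% | 96.4% | 1.3 |

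Gains are taken from unrounded powers.

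**An example.** A primary result of 15/36 against 4/24 (41.7% vs 16.7%, close to the planned rates) has Fisher p = 0.051. Fisher does not reject. Boschloo does, since 0.051 is below c.

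**Sensitivity for the primary comparison.**
- Averaged over a random CIS split with 60% fCIS at N = 60: 64.4% vs 69.4%.
- At N = 54 (32/22): a gain of 3.4 points.
- Doubling the one-sided Boschloo p-value instead: 71.6%, a gain of 6.9 points.
- Fisher needs about 65 completers (39/26, 70.5%) to match Boschloo at 60, so the change is worth about 5 patients.
- At N = 100: Fisher 89.2%, Boschloo 90.7%.

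**The case against.** Fisher's test is pre-specified, familiar and holds 0.05. Choosing a conditional over an unconditional exact test is legitimate, and nothing in the plan contradicts it. Phase II is openly a pilot, so moving its power from about 6% to about 12% changes no conclusion. The planned logistic regression is unaffected. The main weakness of the primary comparison is that the 54 does not come from it, and no change of test cures that. All of this stands. It limits the point to a gain in efficiency, carried mainly by the Phase I primary comparison.

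A reader might infer gains of 10 points or more. Two calculations invite this, and the documents support neither as a planned case.

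- Phase II at 45% vs 15% gives 27.5% vs 40.3%. Those are the Phase I fCIS and pCIS rates. Phase II enrols only pCIS patients, and the protocol expects about 13% against at most about 25%.
- fCIS vs pCIS among patients with good revascularization (18 vs 12, 70% vs 20%) gives 69.7% vs 80.0%. V.B does not name this comparison: its secondary tests compare revascularization within each CIS group. V.A's contrast sets fCIS with good revascularization against all others.

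A reader might also infer that Fisher's test is a mistake here. It is not: its error never exceeds the stated level.

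**Conclusion.** The point holds as an optional, low-cost improvement. Fisher's test uses 1.8% to 3.5% of the nominal 5% in the planned comparisons. Boschloo's test keeps the maximum between 4.3% and 4.9%. At the protocol's own rates it gains about 5 points for the Phase I primary comparison, 3 to 5 for the secondary comparisons, about 6 for Phase II and about 1 for the 0.025 contrast.

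The figures depend on the assumptions listed with the calculation, chiefly two-sided testing and the expected group sizes. Boschloo's error guarantee applies at the realized group sizes, which is acceptable although the CIS split is left free. The change does not bring the primary comparison to the stated 90%: that would take about 100 completers with either test.

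**What to change.** In V.B, before any outcome data are seen, replace the Fisher exact tests for the Phase I primary and secondary comparisons and for Phase II with: Boschloo's unconditional exact test, two-sided, using the two-sided Fisher p-value as the statistic, at 0.05 (0.025 for the contrast of fCIS plus good revascularization against all other groups). Report each risk difference with an unconditional exact confidence interval, and name the interval method.

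The cost is a wording change and a test that some readers know less well. The two-sided definition must be fixed in advance, because primary power is 69.9% or 71.6% depending on that choice. No extra patients are needed, and the stated error limits are kept. The primary comparison's shortfall against 90% power needs separate attention.

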- C. Despite applying the above selection criteria (time from onset of symptoms and findings on CT scan), the percentage of GCO has been consistently lacking behind the recanalization rates which has been steadily improving to up to 80-90%. It is clear that a significant proportion of good revascularizations are futile due to lack of clinical improvement [5-8, 9-12]

Version: 6.0

2

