of good outcomes for these recent trials in the IAT arms have varied widely (52-71%). The investigators believe that a primary factor explaining differences between studies is the portion of people with favorable CIS included in the studies. Interestingly the ratio between the rate of good outcomes in the treatment arm vs. the control arm (no IAT) has been stable across the different positive trials showing the effect of IAT at approximately 1.7 for all of these recent trials, similar to the PROACT II trial more than 15 years ago. [3]. The investigators believe the stagnation of this ratio at 1.7 is evidence that the selection criteria have not improved despite improvement in the rate of revascularization. Based on the existing data, the investigators would like to evaluate the merit of CIS as a primary tool for patient selection in IAT, hoping to prove that the rate of treated to untreated improvement is on the order of 6 to 7. We expect that if we select for patients with fCIS and obtain good revascularization to obtain around 80% GCO in the treated arm. We also expect successful revascularization to be futile for patients with pCIS.

E. The principal investigator believes that the CIS for each patient is determined genetically. In order to explore the genetic link to the CIS, this trial also aims to perform SNP-trait association analysis to identify the genetic loci linked to CIS and stroke outcome in patients suffering from AIS. *Dce1* has recently been found to be responsible for approximately 85% of the variation in collateral extent and it is likely that polymorphisms of *Dce1* are a major determinant of the wide variation in collateral scores in humans. If it is shown that *Dce1* is correlated to CIS and both are predictive outcomes for EVT, then this will further increase confidence in CIS as an assessment of collateral status, strengthen patient stratification of patients to define course of treatment for best outcome and least risk, and suggest the use of genetic testing in clinical decision making.

II. STUDY OBJECTIVE(S); INCLUDING SPECIFIC AIMS AND/OR HYPOTHESES

The hypothesis, or idea being tested, is that as long as patients have a favorable CIS they can be successfully treated with IAT out to 24 hours. For patients with poor CIS, success rates will be relatively low, with no benefit provided by IAT. The long term objective is to:

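### The Phase I secondary endpoint tests revascularization separately by CIS group; with about 2% power in pCIS, a null result there shows neither futility nor a difference in effect

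*Combined protocol and SAP*

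**What the plan says.** Section V.B (Statistical Methodology) makes the fCIS versus pCIS comparison the Phase I primary endpoint. It then gives the secondary endpoint: "The influence of successful revascularization on outcomes for patients with fCIS or pCIS will also be analyzed using Fisher exact tests". No alpha, sidedness, power, effect estimate or confidence interval is attached to this secondary analysis. The logistic regression in the same section lists CIS and mTICI as covariates but specifies no product term between them.

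Section I.D states the expectation that this analysis bears on: "We also expect successful revascularization to be futile for patients with pCIS".

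The planning inputs are in sections III.A and V.A:
- "The sample size will be set to have 60 patients complete the trial"
- "The percentage of patients with fCIS will be 60" (per cent)
- "The percentage of patients with good revascularization will be 50" (per cent)
- "The rate of good outcomes for the combination of pCIS and good revascularization is assumed to be 20" (per cent), against 10% for pCIS with poor revascularization
- 70% and 20% for fCIS with good and poor revascularization

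Sections III.A, V.A and VII.A acknowledge low power for Phase II. Nothing similar is said about the Phase I pCIS comparison.

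**The concern.** The scientific claim is comparative: revascularization helps patients with fCIS and does not help those with pCIS. Two separate significance tests do not address it. Finding p below 0.05 in one group and above 0.05 in the other is not a test of whether the two effects differ. In the smaller group with the lower event rate, a non-significant result says almost nothing about whether an effect is absent.

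Everyone in Phase I receives IAT, so the comparison of good with poor revascularization, by CIS group, is the only within-phase evidence on whether CIS modifies the effect of revascularization. An uninformative pCIS result could be reported as support for the expectation in section I.D.

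**Working it through.** **The plan's own figure.** Section V.A gives 54 patients for 90% power, with alpha 0.025 for fCIS with good revascularization against everyone else. The first group is 0.6 × 0.5 = 30% of patients, with rate 0.70. The other three cells are 30%, 20% and 20% of patients, with rates 0.20, 0.20 and 0.10, so their pooled rate is (0.06 + 0.04 + 0.02)/0.70 = 0.1714. The two-proportion formula with two-sided alpha 0.025, power 0.90, allocation ratio 0.7/0.3 and continuity correction gives 16 + 38 = 54. The stated figure is reproduced, which supports this reading of the inputs. It does not size the within-group tests.

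**Expected cells at 60 completers.**
- fCIS: 60 × 0.6 × 0.5 = 18 good vs 18 poor revascularization
- pCIS: 60 × 0.4 × 0.5 = 12 vs 12

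**Power of each Fisher test.** Power is the sum, over all pairs (a, b) with Fisher p ≤ 0.05, of Bin(a; n₁, p₁) × Bin(b; n₂, p₂). Two-sided 0.05 is assumed.

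| Group | Cells | Rates | Power |
|---|---|---|---|
| fCIS | 18 vs 18 | 70% vs 20% | 0.835 |
| pCIS | 12 vs 12 | 20% vs 10% | 0.022 |
| pCIS | 12 vs 12 | 30% vs 10% | 0.095 |
| pCIS | 12 vs 12 | 40% vs 10% | 0.233 |
| pCIS | 12 vs 12 | 50% vs 10% | 0.425 |

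With 0, 1 or 2 good outcomes among 12 poorly revascularized pCIS patients, significance needs at least 5, 7 or 8 of 12 in the other cell. For 80% power at 20% vs 10%, about 199 per cell would be needed (219 with continuity correction).

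**Sensitivity of the 2.2% (20% vs 10% throughout).**
- One-sided 0.05: 6.6%
- Two-sided 0.025: 0.6%
- 24 pCIS patients split at random 50/50: 3.3%
- pCIS at 30% of patients (9 vs 9): 0.9%
- pCIS at 70% of patients (21 vs 21): 7.9%, or 12% one-sided

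**How often fCIS alone is significant.** The groups contain different patients, so the probability is fCIS power × (1 − pCIS power).
- Plan's rates: 0.835 × (1 − 0.022) = 0.82
- Equal odds ratios: OR = (0.7/0.3)/(0.2/0.8) = 9.33. Applied to 10%, the odds are 9.33 × 0.1/0.9 = 1.037 and the rate is 0.509. pCIS power is 0.444, so 0.835 × 0.556 = 0.46
- Equal risk differences (60% vs 10%): pCIS power is 0.639, so 0.835 × 0.361 = 0.30

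**What a direct contrast would deliver.** The difference between risk differences is (0.70 − 0.20) − (0.20 − 0.10) = 0.40. Its SE is √(0.21/18 + 0.16/18 + 0.16/12 + 0.09/12) = √0.0414 = 0.203, so z = 1.97 and power is about 50%. On the log-odds scale the contrast is ln(9.33/2.25) = 1.42. Its SE is √[1/(18 × 0.21) + 1/(18 × 0.16) + 1/(12 × 0.16) + 1/(12 × 0.09)] = 1.43, so z = 0.99 and power is about 17% (Wald approximation).

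**What the pCIS data would look like.** An observed 2/12 vs 1/12 has a risk difference of +8 points, with a Newcombe 95% CI of about −21 to +37.

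**The case against.** Several points can fairly be made for the plan.

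- **A reader might infer that the pCIS test decides whether IAT is withheld in Phase II.** The documents do not support that. Sections III.A, VI.A and VIII.B tie the launch to the good-outcome rate in treated pCIS patients and to the safety committee's review. Phase II then randomizes pCIS patients with and without IAT. Nor does any section say that a non-significant test will be called futility; section I.D states an expectation.
- **A reader might say that assuming 20% vs 10% contradicts expected futility.** That goes too far. Section I.D judges pCIS against roughly 20% good outcomes in untreated patients, and section V.A mentions 25%. A 20% rate after good revascularization is no better than those benchmarks. The point here is narrower: the test cannot detect the difference that the plan itself assumes.
- **A reader might treat 80-90% revascularization as the plan's own value.** Section I.C speaks of "recanalization rates which has been steadily improving to up to 80-90" per cent as background; the planning value is 50%. As a sensitivity scenario only, 80-90% would lower fCIS power to about 63-43%, pCIS power to below 0.5%, and the additive contrast to about 39-25%.
- **CIS and revascularization are used jointly elsewhere.** The sized comparison sets fCIS with good revascularization against all other patients, and the regression includes both variables. Neither tests whether the effect of revascularization differs by CIS.
- **The replacement is imprecise too.** This stands. Its merit is that it addresses the right question and shows the uncertainty.

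**Conclusion.** The concern holds as a matter of analysis and interpretation. On the plan's inputs, the pCIS test will be non-significant about 98% of the time although the assumed good-outcome rate doubles, so that result cannot support futility. Significance in fCIS alone is the expected pattern on the plan's rates (82%). It also arises in a substantial minority of trials when the effect is the same in both groups (46% or 30%, depending on the scale), so it cannot establish effect modification.

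This rests on reading the endpoint as one test per CIS group, which is natural but not spelled out, on cells of the expected size, and on a two-sided 0.05 level. The conclusion for pCIS does not depend on the last two: at 20% vs 10%, power was 12% or less in every variant run. The change should be made. It concerns a secondary endpoint and does not undermine the Phase II launch criteria.

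**What to change.** In section V.B, replace the pair of Fisher tests as the secondary analysis with one prespecified CIS-by-revascularization contrast: the risk difference (good minus poor revascularization) in fCIS minus that in pCIS, with a 95% CI and a named interval method. Alongside it:

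1. Report the risk difference with its 95% CI within each CIS group.
2. State that a non-significant pCIS result will not be interpreted as futility.
3. State the alpha and sidedness, and disclose the low power of the pCIS comparison (about 2% at 20% vs 10%), as is already done for Phase II.
4. Optionally, show power at 80-90% revascularization, labelled as a sensitivity scenario.

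The cost is a change to the analysis text and one extra estimate, with no additional patients or data. The downside is that the conclusion becomes visibly less certain, because the contrast has only about 50% power on the risk-difference scale and about 17% on the log-odds scale.
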